- VII.B.11** *Is there a separate, written protocol that will be submitted in addition to this IRB New Project form? (Note: a grant application is not considered to be a protocol)*
No
- VII.B.18** *Does this project involve testing the safety and/or efficacy of a medical device?*
Yes
- VII.B.19** *Describe in detail procedures in place for maintaining device shipment and receipt records:*
This device is already onsite being used in the UIHC Main Operating Room and Pediatric Catheter Laboratory of alternative purposes, thus, no device shipping or receipt will occur.
- VII.B.20** *Who will be responsible for maintaining these shipment and receipt records?*
N/A
- VII.B.21** *Describe in detail procedures in place for tracking use and disposition of devices described in this study:*
N/A

- VII.B.22 ***Who will be responsible for maintaining these use and disposition tracking records?***
N/A
- VII.B.23 ***Describe in detail procedures in place to limit access to authorized study personnel for the storage, control, and dispensing of the investigational devices. (For example, investigational devices are kept in a locked area away from approved devices or have a keyed interlock, and only study personnel authorized to dispense the device have the keys)***
N/A
- VII.B.24 ***Is the device FDA-approved for the way it will be used in this study?***
No
- VII.B.25 ***Is there an IDE (Investigational Device Exemption) for this device in this research project?***
No
- VII.B.29 ***Indicate the appropriate FDA status you and/or the sponsor are requesting for the use of this device in this study.***
Non-Significant Risk (NSR) device/software
- VII.B.31 ***Provide a detailed rationale for why this device meets the FDA definition of a Non-Significant Risk Device (NSR)***
Because it is not intended as an implant nor is it to be used in supporting or sustaining human life. At this time it is not of substantial importance in diagnosing, curing, mitigating or treating disease.
- VII.B.32 ***Provide a summary of prior investigations with this device.***

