TEE is routinely used in cardiothoracic and interventional surgeries as well as in detecting thromboses, valvular defects and congenital heart disease. TEE is used nearly universally in cardiac surgical operating rooms and exhibits a low risk of complications (Daniel 1991). While it has been shown that TEE can be used to visualize the spinal column when attempted (Chitilian 2006), TEE has never been used to confirm the placement of epidural catheters using this new window of view. Because epidural catheters are usually blindly threaded, we would like to assess the sensitivity and specificity achieved by TEE in correlating confirmation of an epidural catheter at targeted thoracic spinal levels and the efficacy of that catheter.

VII.C. Project Description (C)

VII.C.1 *Does this project involve any [research on genes or genetic testing/research?](#)*

No

VII.D. Project Description (D)

VII.D.1 *Check all materials/methods that will be used in recruiting subjects (you will need to attach copies of all materials at the end of the application):*

Use of any information available to the researchers or their colleagues because this person is a patient OR use of any information considered to be Protected Health Information (PHI) OR review of patient/clinic records - Operating room schedule

Referral from colleague - Thoracic surgery physicians and nurses may identify potential patients. Also, some patients may be identified by Pre-Anesthesia Evaluation Clinic staff.

VII.D.2 *List the individual data elements you will need to access/use from the patient or clinic records to identify potential subjects for recruitment*

We will need to access patient records to check the patient's eligibility for the study by checking their surgical procedure, past medical history, counter indications for TEE use intra-operatively (esophageal trauma, lesion or disease) and age.

VII.D.3 *Describe why you could not practicably recruit subjects without access to and use of the information described above*

Many patients may be unaware that they are eligible for the study because they do not understand the routine use of TEE in the operating room. They

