degree toward the descending aorta, with adjusted gain and depth in order to obtain the best image of the spinal cord and epidural space possible. A trained TEE operator (either an anesthesiologist or cardiologist) will control the machine and obtain an image of the spinal canal at the targeted vertebral level. They will then capture an image of the spinal canal at this level. A different anesthesiologist will begin placement of a thoracic epidural catheter, as is standard protocol for anesthesia, however, these catheters are normally threaded blindly. In our study, catheter placement will occur with the assistance of the TEE operator to confirm the catheter is advanced to target level. The real-time TEE image generated will allow for confirmation of the catheter within the epidural space at this point. Further, when the anesthesiologist believes they have reached the targeted thoracic level, they will inject 1 mL of normal saline to assess intrathecal spread in the epidural space. When the catheter is threaded to sufficient targeted level, as determined by the anesthesiologist, a bolus dosage of anesthetic will be given (0.4 mL/kg of 1.5% Lidocaine) again, this is all standard procedure in these surgeries. Because it is standard procedure for epidural catheter to be placed blindly prior to surgery, we hope to determine whether the use of TEE for guidance and confirmation will actually improve the results and decrease the time needed to ensure adequate placement. Anesthesiologists will be given three attempts to use TEE for confirmation. The anesthesiologist will be able to see the image on TEE, and the trained TEE monitor will be allowed to discuss images seen on the ultrasound screen.

At this time, the trained TEE operator will assess the location of the epidural catheter within the epidural space at target level on real-time TEE images as anterior, posterior or lateral to the spinal cord. Further, the TEE operator will take images of the catheter confirmed at the target spinal level in order to later compare with the images taken prior to catheter threading.

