The time period for the pre-operative procedure will require approximately thirty minutes but will not extend patient time in the operating room or catheter laboratory as all procedures will occur as the patient is being prepared for surgery and this would occur normally by the anesthesia team.

No additional visits or extra time is required of the subject. There will be no necessary long-term follow up or data collection. When the patient leaves the operating room, nothing additional is required.

VII.E.7 *Will you attempt to recontact subjects who are lost to follow-up?*

No - followup is not required in this study

VII.E.9 *Will subjects be provided any compensation for participating in this study?*

No

VIII. Risks

VIII.1 *What are the risks to subjects including*

- *emotional or psychological*
- *financial*
- *legal or social*
- *physical?*

The care the patient will receive is standard practice at UIHC for cardiothoracic surgery or interventional cardiology diagnostic procedures under general anesthesia and are necessary procedures regardless of this research study. The postoperative x-ray would occur to visualize the heart, regardless of study participation thus, no additional exposure to ionizing radiation is incurred by participation. The only potential additional physical

risk involved is an increased risk of esophageal trauma as the TEE probe may be maneuvered more than normal to observe catheter entry and anesthetic spread. The low risk of esophageal injury associated with TEE makes this unlikely but it is still a possibility that must be noted. Patients ******(and parents)****** may be under slightly elevated emotional stress knowing that they are part of a research study. There is a very low risk of loss of confidentiality of the patient's medical information, yet this is unlikely as patients will be given identification numbers at the earliest date possible and these will only be accessed by members of the research team. Only the data necessary to answer the research question will be collected upon reviewing patient information. There are no other known financial, physical or legal risks to the patient.

- VIII.2** ***What have you done to minimize the risks?***
If applicable to this study ALSO include:
How you (members of your research team at Iowa) will monitor the safety of individual subjects.

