Include a description of the availability of medical or psychological resources that subjects might require as a consequence of participating in this research and how referral will occur if necessary (e.g. availability of emergency medical care, psychological counseling, etc.)

Healthcare professionals will monitor the subject at all times during the operation. The patient will be reassured that although they are participating in the study, everything that happens during the case is already standard practice at UIHC for cardiothoracic surgery or interventional cardiology diagnostic procedures under general anesthesia. TEE probe maneuvering will only be done as necessary to minimize any physical trauma beyond what is already standard procedure in these patients. All patients will be given an identification number and be referred to by such. To prevent loss of confidentiality of the patient's medical information, we will keep all records used for this study in a locked office or on password protected computer system. Only members of the research team will have access to the records used in this study. No key will be kept as patients will not need to be contacted in the future.

- VIII.3** ***Does this study have a plan to have an individual or committee review combined data from all subjects on a periodic basis (such as summary or aggregate safety and/or efficacy data)?***

No

IX. Benefits

- IX.1** ***What are the direct benefits to the subject (do not include compensation or hypothesized results)?***

There are no direct benefits to the subject.

- IX.2** ***What are the potential benefits to society in terms of knowledge to be gained as a result of this project?***

This novel method to visually confirm epidural catheter placement and anesthetic spread within the epidural space could greatly increase the safety and success rate of epidural analgesia. Further, it provides an alternative to the ionizing radiation and contrast injection used in current methods of fluoroscopy to confirm catheter placement. By determining the success rate achieved using TEE as an alternative method to thread and confirm epidural catheter placement, it will allow us to compare with current techniques already in use and potentially improve patient safety and care.

X. Privacy & Confidentiality

X.1 *What are you doing to protect the privacy interests of the subjects?*

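### The reassurance in VIII.2 that the whole case is standard practice is inaccurate on the form's own terms and could undercut the risk explanation promised at consent

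*Combined protocol and SAP*

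**What the plan says.** Section VIII.2 asks what has been done to minimise risks. After noting that the child is monitored throughout the operation, it gives this step: "The patient will be reassured that although they are participating in the study", "everything that happens during the case is already standard practice at UIHC". Its next sentence limits probe movement to what is necessary and refers to trauma over and above the standard procedure. The rest of the paragraph concerns confidentiality.

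Elsewhere the form describes what the study adds:

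- **VIII.1 (risks):** it opens with "The care the patient will receive is standard practice at UIHC for cardiothoracic surgery", and then says that the only additional physical "risk involved is an increased risk of esophageal trauma as the TEE probe may be maneuvered more than normal".
- **VII.B.37 (difference from the approved use):** "TEE has never been used to confirm the placement of epidural catheters using this new window of view".
- **VII.E.6 (procedures):** "these catheters are normally threaded blindly. In our study, catheter placement will occur with the assistance of the TEE operator".
- **VII.D.30 (parental consent):** on both the clinic route and the day-of-surgery route, the team will explain benefits and risks and hand over a consent document that carries a study contact.
- **ROC.5 (key complications):** it mentions a sore throat lasting a few hours, and not esophageal trauma.

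**The concern.** A statement listed as a protection for subjects should at least be true. This one covers everything in the case, which leaves no room for the part that is research. The distinction a family has to grasp is between care the child would receive anyway and what the study adds. The reassurance removes that distinction.

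It matters more here because IX.1 states that there is no direct benefit to the subject, so any added risk is central to the decision. Families approached on the day of surgery have one to two hours to decide (VII.D.27), which is little time to resolve two conflicting messages.

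**Working it through.** No arithmetic applies, since the point depends on no rate, effect size or sample size. The check is to set the reassurance against each component of the case.

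| Component | How the form describes it | Does the VIII.2 reassurance fit? |
|---|---|---|
| Surgery or catheter-laboratory procedure, general anesthesia | Standard, needed regardless of the study (VIII.1) | Yes |
| TEE probe placed to view the heart | Standard in these cases (VII.E.6) | Yes |
| Epidural catheter and anesthetic bolus | Standard (VII.E.6) | Yes |
| Post-operative x-ray | Would be taken anyway (VIII.1) | Yes |
| TEE used to guide and confirm the catheter | Not done before (VII.B.37); usual practice is blind threading (VII.E.6) | No |
| Probe movement for that purpose | May exceed the normal amount, with increased esophageal risk (VIII.1) | No |

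The last two rows are the study intervention. VII.E.6 shows why the extra movement belongs to the research: the probe is first placed to view the heart, is turned by about 180 degrees to image the spinal canal, and goes back to its cardiac position once the catheter work is finished.

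**Can the sentence be read more narrowly?** VIII.1 also begins by calling the care standard, but it then names the exception. VIII.2 names no exception within the reassurance. The sentence that follows, on limiting probe movement, concedes that trauma beyond the standard procedure is possible, so the two adjacent sentences do not agree either.

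**Who hears it?** VIII.2 says the patient. Parents give consent, but VII.D.30 uses the word patients for those who sign the consent document, and VII.D.36 has children aged 7 to 12 sign assent and those over 12 sign consent. On either reading the statement can reach someone who is being asked to agree.

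**How many?** The form plans to enrol 25 minors (VI.6, VI.13) and to stop once data are collected in 20 (VI.15). The reassurance is not restricted to a subgroup.

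**The case against.** The other side has real force on several points.

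- **Consent covers the risk.** VII.D.30 promises an explanation of risks on both routes, with a document. A reader might infer from VIII.2 that families are misinformed. The documents do not show that: the consent document is not in the available text, and VIII.2 gives neither a script nor a time for the reassurance. What stands is that a sound disclosure in one place does not make an inaccurate statement in another acceptable.
- **The sentence may answer a different risk.** VIII.1 also says that patients and parents "may be under slightly elevated emotional stress knowing that they are part of a research study". The reassurance may be meant for that, with the following sentence addressing trauma. This is plausible, and it means that VIII.2 does contain a genuine mitigation of the physical risk. It does not make the reassurance accurate.
- **Lack of FDA approval is a separate matter.** VII.B.24 asks "Is the device FDA-approved for the way it will be used in this study" and the answer is No. A reader might count this as a further contradiction, but regulatory approval of a use is a different question from what is standard at the hospital. The point does not rest on it.
- **Harms could still reach the team.** A reader might infer that a family told all was routine would not report a problem, and that it would then go unseen. The documents do not support so strong a claim: VII.E.6 collects pain scores after surgery and at 24 hours and morphine use over 24 hours, ROC.4 provides for a 24/7 contact for complications, and the consent document carries a contact. None of these data items is specific to esophageal injury, but the routes exist.

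**Conclusion.** The concern holds in limited form. The planned reassurance is inaccurate when set beside VIII.1, VII.B.37 and VII.E.6, and it could undercut the risk explanation promised in VII.D.30. The risk it glosses over is the only additional physical risk that the form names; VIII.1 also lists emotional stress and loss of confidentiality, so it is not the only risk of participation.

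The statement applies to all enrolled children, up to 25. That is the planned enrolment and does not measure any effect on families' decisions, which the documents give no means to estimate. The endpoint, sample size and analysis are untouched. The conclusion rests on reading the reassurance as something that will be said, as VIII.2 states, and it assumes nothing about the content of the consent document. The correction is worth making because it concerns what subjects are told and costs almost nothing.

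**What to change.** In VIII.2, replace the blanket reassurance with a statement along these lines: the surgery, routine TEE, epidural and post-operative x-ray are described as standard care at this hospital; using TEE to guide the catheter, and the extra probe movement that this involves, are research and may add to the risk of esophageal trauma as stated in VIII.1.

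Then:

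1. Keep the existing limit on probe movement, which is the real mitigation in that paragraph.
2. Point families to the contact already on the consent document.
3. Check that the consent document and ROC.5 describe the added risk consistently with VIII.1. ROC.5 at present mentions only a sore throat.

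The cost is the rewording of one paragraph and a consistency check of two other texts. No procedure, sample size or analysis changes. A small downside is that some families may decline when the research component is stated plainly.
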